### **Model Checking and Diagnostics**

Convergence diagnostics via scale reduction factors (Rhat), effective sample size, and posterior predictive distributions will be examined to ensure satisfaction of Bayesian modeling assumptions, including Rhat  $< 1.01$ , sufficiently large effective sample size, and graphical inspection that the observed distribution of each outcome fell within the range of distributions produced by 1000 replications drawn from the posterior predictive distributions of the outcome.

Adequate values for the number of MCM samples/thinning/number of burn-in samples should be chosen to ensure that the ratio Monte Carlo Standard Errors (MCSE) and standard deviation of the posterior distribution for all the parameters in the model as small as possible, typically close to 0.01.

In addition, if possible, the number of tuning units and maximum number of tuning iterations may be increased to find a better proposal distribution for the model parameters, which in turn may reduce the MCSE/SD ratio.

The Geweke diagnostics test checks whether the mean estimates have converged by comparing means from the early and latter part of the Markov chain using a z score t-test. Large absolute values of the z-score statistic indicate rejection of the null hypothesis of no difference between the mean estimates obtained from the early and latter parts of the chain.

The convergence diagnostics for all parameters in the Bayesian analysis will be visually checked by the trace plots.

If the trace plots show apparent trend or the autocorrelation plots show significant positive or negative correlation, number of iterations will be increased or reparameterization might be explored.

### **Results presentation**

Presentation of results from the Bayesian statistical models will include the estimated conditional/marginal mean treatment effects and standard deviation. For all endpoints analysed statistically, estimated mean treatment differences will be presented together with 95% credible intervals and posterior probabilities.

Bayesian Method 2 Endpoint/Variable
Change from baseline in Multiple Sclerosis Quality of Life (MSQOL)-54 Composite scores following treatment with HB-adMSCs or Placebo at Week 4, Week 8, Week 16, Week 24, Week 32, Week 42 and Week 52.
Bayesian model specification
Construct a linear model for each visit in order to model within-subject observation covariance structures by multivariate normal (MVN) distribution in the MCM procedure.
For subject i on treatment j at Visit k, the model can be written as: $CHG_{ijk} = \beta_0 + \beta_1 \text{treatment} + \beta_2 \text{baseline} + \beta_3 \text{Visit}_k + \beta_3 \text{strataEDSS} + \beta_4 \text{strataAge} + \beta_5 \text{strataGender} + \varepsilon_{ijk} \quad \varepsilon_{ijk} \sim \text{Normal}(0, \sigma^2)$ Where $CHG_{ijk}$ refers to change from baseline in subject $i = 1, 2, \dots, n$ and $\text{Visit}_k$ for $k = 1, 2, 3, 4, 5, 6$ represents Week 4, Week 8, Week 16, Week 24, Week 32, Week 42 and Week 52, respectively are indicator variables, which are intrinsically formed within PROC MCMC from the design matrix.
Initial values of the MCMC chains will be selected at random. Seed for random number generation will be specified as "seed = 12345" with three MCMC chains of 8000 total iterations each (with 4000 of these discarded as burn-in iterations). The simulation size and number of burn-in iterations can be updated during the convergence check.
The choice of prior distribution for level two variances will follow Gelman's recommendations from the literature. Models will use weakly informative priors to maximize the influence of the present data on posterior probabilities (PP). The non-informative priors for the model parameters $\sim \text{Normal}(0, \sigma^2 = 10)$ and $1/\sigma^2 \sim \text{Gamma}(0.001, \text{rate} = 0.001)$ will be used.
Models were evaluated via posterior probability guidelines in the literature, suggesting that $PP = 75\%$ to $90\%$ indicates "moderate evidence," $PP = 91\%$ to $96\%$ indicates "strong evidence," and $PP \geq 97\%$ indicates "very strong to extreme evidence." Consistent with prior research, a $PP \geq 75\%$ (equivalent to a Bayes factor = 0.33 or 3.00) that an effect exists will be taken as a minimum threshold of evidence in favor of the alternative hypothesis. This probability was chosen to emphasize the value in identifying a signal for the effects of treatment group, time, and their interaction.
The median, standard deviation, and 95% credible intervals (CrI) of the posterior distribution will be used to provide a point estimate and corresponding range of uncertainty for the magnitude of each predictor effect, including treatment group.
Model Checking and Diagnostics
Convergence diagnostics via scale reduction factors (Rhat), effective sample size, and posterior predictive distributions will be examined to ensure satisfaction of Bayesian

modeiling assumptions, including  $Rhat < 1.01$ , sufficiently large effective sample size, and graphical inspection that the observed distribution of each outcome fell within the range of distributions produced by 1000 replications drawn from the posterior predictive distributions of the outcome.

Adequate values for the number of MCM samples/thinning/number of burn-in samples should be chosen to ensure that the ratio Monte Carlo Standard Errors (MCSE) and standard deviation of the posterior distribution for all the parameters in the model as small as possible, typically close to 0.01.

In addition, if possible, the number of tuning units and maximum number of tuning iterations may be increased to find a better proposal distribution for the model parameters, which in turn may reduce the MCSE/SD ratio.

The Geweke diagnostics test checks whether the mean estimates have converged by comparing means from the early and latter part of the Markov chain using a z score t-test. Large absolute values of the z-score statistic indicate rejection of the null hypothesis of no difference between the mean estimates obtained from the early and latter parts of the chain.

The convergence diagnostics for all parameters in the Bayesian analysis will be visually checked by the trace plots.

If the trace plots show apparent trend or the autocorrection plots show significant positive or negative correlation, number of iterations will be increased or reparameterization might be explored.

### **Results presentation**

Presentation of results from the Bayesian statistical models will include the estimated conditional/marginal mean treatment effects and standard deviation. For all endpoints analysed statistically, estimated mean treatment differences will be presented together with 95% credible intervals and posterior probabilities.

## **5.3. Secondary Endpoint(s) Analyses**

### **5.3.1. Efficacy Endpoints / Variables**

- Change from baseline at Week 52 in Total Expanded Disability Status Scale (EDSS) scores following treatment with HB- adMSCs or Placebo
- Change from baseline at Week 52 in Barthel Index scores following treatment with HB- adMSCs or Placebo
- Change from baseline at Week 52 in 9-Hole Peg Test scores following treatment with HB- adMSCs or Placebo
- Change from baseline at Week 52 in Patient Health Questionnaire (PHQ-9) scores following treatment with HB-adMSCs or Placebo

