Laboratory Samples.	
Screening, Week 0, 24 and 52.
 
Screening
 
Week 0 – Infusion 1
 
Week 4 – Infusion 2
 
Week 8 – Infusion 3
 
Week 16 – Infusion 4
 
Week 24 – Infusion 5
 
Week 32 – Infusion 6

Visits by Weeks	

Week 42 – Follow Up.

Week 52 – End of Study

“A Randomized, Double-Blind, Single Center, Phase 2, Efficacy and Safety Study of autologous HB-adMSCs vs Placebo for the Treatment of Patients with Multiple Sclerosis”

Objectives

Primary Objective

- To investigate the efficacy of intravenous infusions of HB-adMSCs vs Placebo in patients with Multiple Sclerosis as determined by improvements in Multiple Sclerosis Quality of Life (MSQOL)-54 Instrument. (Time frame: Baseline to Week 52).

Secondary Objectives

- To evaluate the efficacy of intravenous infusions of HB-adMSCs vs. Placebo in patients with Multiple Sclerosis as determined by changes in Expanded Disability Status Scale (EDSS) (Time frame: Baseline to Week 52).
- To assess the efficacy of intravenous infusions of HB-adMSCs vs. Placebo in patients with Multiple Sclerosis as determined by changes in The Barthel Index (Time frame: Baseline to Week 52).
- To determine the efficacy of intravenous infusions of HB-adMSCs vs. Placebo in patients with Multiple Sclerosis as determined by changes in 9-Hole Peg Test (Time frame: Baseline to Week 52).
- To identify the safety of intravenous infusions of HB-adMSCs vs. Placebo in patients with Multiple Sclerosis as determined by changes in Patient Health Questionnaire (PHQ-9) (Time frame: Baseline to Week 52).
- To assess the safety of intravenous infusions of HB-adMSCs vs. Placebo in patients with Multiple Sclerosis as determined by the incidence of adverse events or serious adverse events (Time frame: Baseline to Week 52).

Endpoints

Primary Endpoints

The safety and efficacy endpoints of this study will be evaluated by assessing changes from Baseline to Weeks 52 in the following:

- Multiple Sclerosis Quality of Life (MSQOL)-54 Instrument. This 54-item questionnaire provides 12 subscales, two summary scores, and two extra single-item measures. The subscales are physical function, role limits-physical, emotional role restrictions, pain, emotional well-being, energy, health perceptions, social function, cognitive function, health distress, overall quality of life, and sexual function.
- Incidence of treatment-emergent Adverse Event (TEAEs) and serious Adverse Events (SAEs).

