The MSQOL-54 is a comprehensive health-related quality of life measure incorporating general and MS-specific questions into a single instrument. The developers used the SF-36 as a base and added 18 questions to address MS-specific problems, including fatigue and cognitive function. This 54-item questionnaire provides 12 subscales, two summary scores, and two extra single-item measures. The subscales are physical function, role limits-physical, emotional role restrictions, pain, emotional well-being, energy, health perceptions, social position, cognitive function, health distress, overall quality of life, and sexual function (National Multiple Sclerosis Society, 2021).

The Barthel Index

When it comes to patients with chronic, debilitating illnesses, the Barthel index is an ordinal scale that evaluates functional independence in the domains of personal care and mobility. A total of ten variables describing activities of daily living and mobility are considered, with a higher number reflecting better capacity to operate independently. The Barthel Index assesses the level of help needed by a person on a set of ten activities of daily living (ADL) related to mobility and self-care (Elite Learning, 2008).

9-Hole Peg test

The 9-HPT is a short, standardized upper extremity exam. In MS research, gait analysis has been given precedence over arm and hand function analysis. In recent years, clinical investigations have increasingly recognized the value of assessing arm and hand function, particularly in severely disabled patients. The 9-HPT has recently become one of the most widely utilized upper extremity measurements in MS. Many qualified examiners can administer the 9-HPT since it is short and standardized. (National Multiple Sclerosis Society, 2021).

PHQ-9 (Patient Health Questionnaire-9)

Suicide prevention programs may also have a clinical component, which refers to how individuals are evaluated and treated for mental health problems or suicidal thoughts in medical facilities. The PHQ-9 is the most used depression and suicidal thoughts screening test. Other

screening methods exist, although some are tailored to certain populations or situations. The Patient Health Questionnaire (PHQ) is a self-administered version of the PRIME-MD diagnostic tool for common mental illnesses (Kroenke, 2001).

Physical Examinations

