If an infusion is stopped for a subject due to an adverse event or serious adverse event, including but not limited to hypersensitivity reaction/anaphylaxis, no additional study treatment will be given to the study participant who develops the event. Although, the study participant will not receive the investigational product, he or she must be followed for safety purposes according to the protocol.

Study Stopping Rules

This Clinical Trial will stop if any of the following events are present:

1. Subject's Death.
2. Occurrence of any thromboembolic event during or after HB-adMSCs administrations (up to 72 hours).
3. Any cerebrovascular ischemia or seizure event occurring within 72 hours after any of the investigational product administrations.
4. Any Serious Adverse Events determined to be related to the following:

- When there is one CTCAE.v5 grade 4 or 5 AE, irrespective of attribution.
- Either any CTCAE Grade 2 adverse event that persists for more than two weeks, or any Grade 3 adverse event, that occurs within 72 hours after product administration.

Should the study participant discontinue study treatment he/she will be followed for safety according to the protocol safety monitoring plan. The study participant will receive follow up communication via phone calls and/or electronically to ascertain the outcome until resolved fully. All will be documented as per protocol.

All changes to the study stopping rules shall be reviewed by FDA. If the study is suspended for any reason, it will not be re-opened until FDA agrees. Regardless of whether the study is stopped or suspended all subjects will be followed to the EOS as per protocol.

Statistical Methods

Sample size consists of up to 24 subjects who have been diagnosed with Relapsing Remitting Multiple Sclerosis. All data collected from subjects who are enrolled and received the investigational product will be analyzed. The incidence of Adverse Events and Serious Adverse Events will be recorded and reported. Efficacy will be measured by improvement of subject's signs and symptoms associated with Multiple Sclerosis. Interim analysis of all safety and efficacy data may be performed at any time deemed appropriate by the Sponsor. Although, the subject's data may be analyzed at any time, a data analysis of all available data will be conducted when a least 10 subjects in each group have completed Week 24. Data may be analyzed for internal informational purposes, reports, presentations, and manuscripts.

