

• To identify the safety of intravenous infusions of HB-adMSCs vs. Placebo in patients with Multiple Sclerosis as determined by changes in Patient Health Questionnaire (PHQ-9) (Time frame: Baseline to Week 52).

• To assess the safety of intravenous infusions of HB-adMSCs vs. Placebo in patients with Multiple Sclerosis as determined by the incidence of adverse events or serious adverse events (Time frame: Baseline to Week 52).

	

• Change from baseline at Week 52 in Patient Health Questionnaire (PHQ-9) scores following treatment with HB-adMSCs or Placebo

• Incidence of treatment-emergent Adverse Event (TEAEs) and serious Adverse Events (SAEs)

• Incidence and risk of AEs of special interest (serious or nonserious), including thromboembolic events, peripheral events defined as, thromboembolism of the extremities, also infections and hypersensitivities.

• Clinically significant changes in laboratory values, vital signs, weight, physical examination results and Multiple Sclerosis concomitant medications.

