## 4. ANALYSIS SETS

Population	Definition / Criteria	Analyses Evaluated
Safety analysis set	

• All randomised subjects who received at least one dose of HB-adMSCs infusion or placebo.

• If participants receive a treatment different to their randomized treatment, they will be analysed according to the treatment actually received.

	

• Safety

• Study Population

Efficacy analysis set	

• All randomized participants who received all 6 infusions of HB-adMSCs or placebo.

• Participants will be analysed according to their randomized treatment.

	

• Efficacy

Screened Population	

• This population consists of all subjects who signed an ICF to participate in the clinical trial.

• This population will be used for summarizing screening failures and reasons for screening failures.

	

• Study Population

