### **Additional analysis**

Summary analysis will be performed to compare difference between baseline to Week 4, Week 8, Week 16, Week 24, Week 32, Week 42 and Week 52, a paired t-test performed for secondary efficacy endpoints above as given in the Section [5.2.2](#).

To further evaluate if the improvements are clinically relevant, effect size of the treatment difference at Week 4, Week 8, Week 16, Week 24, Week 32, Week 42 and Week 52, Cohen's d will also be calculated for the secondary efficacy endpoints as given in the Section [5.2.2](#).

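### PHQ-9 change measures a safety objective, but the SAP files it under efficacy, which implies the six-infusion set and omits early stoppers who complete the Week 52 form

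*SAP*

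**What the plan says.** The protocol's Secondary Objectives include "To identify the safety of intravenous infusions of HB-adMSCs vs. Placebo in patients with Multiple Sclerosis as determined by changes in Patient Health Questionnaire (PHQ-9". SAP section 2.1 repeats this as a safety objective, "as determined by changes in Patient Health Questionnaire (PHQ-9) (Time frame: Baseline to Week 52". The protocol's description of the instrument says "The PHQ-9 is the most used depression and suicidal thoughts screening test".

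SAP section 5.3.1, headed as efficacy endpoints, lists "Change from baseline at Week 52 in Patient Health Questionnaire (PHQ-9) scores following treatment with HB-adMSCs or Placebo" beside EDSS, the Barthel Index and the 9-Hole Peg Test. All four get the same methods: a repeated measures model as the main analysis, ANCOVA as the second, paired t-tests, and an effect size ("Cohen's d will also be calculated for the secondary efficacy endpoints").

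SAP section 4 defines two treated sets. The Efficacy set, assigned to efficacy analyses, is "All randomized participants who received all 6 infusions of HB-adMSCs or placebo", grouped as randomised. The Safety set, assigned to safety analyses, needs only one dose and groups patients by treatment received.

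Under the protocol's Infusion Stopping Rules, if an infusion is stopped for an adverse event, "no additional study treatment will be given to the study participant who develops the event", but "he or she must be followed for safety purposes according to the protocol". The schedule of assessments takes PHQ-9 at Week 0 and Week 52 only.

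SAP sections 5.3.2 and 5.3.3 cover exposure, adverse events, laboratory data, physical examination and vital signs. Neither names PHQ-9.

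**The concern.** A safety measure should be read in everyone exposed. If PHQ-9 follows its efficacy label, membership of the analysis depends on having received the full course, and one reason for not receiving it is an adverse event. The safety objective would then be answered only in patients who had all six infusions.

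This also sits badly with the protocol's Statistical Methods section, which says that data from all enrolled subjects who received the product will be analysed. SAP section 5.4 nevertheless declares no departure from the protocol's analyses.

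The second issue is resolution. The protocol describes the instrument partly as a screen for suicidal thoughts, but the planned analyses work on scores. A change confined to one item in one patient is not displayed by any PHQ-9 analysis that the SAP names.

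**Working it through.** The documents state no figure for PHQ-9, so there is none to reproduce. The check is a reading of the text, followed by an illustration.

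**Which patients are analysed**

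1. PHQ-9 change serves a safety objective (protocol Secondary Objectives; SAP 2.1).
2. SAP 5.3.1 places it under efficacy without naming a set.
3. SAP 4 assigns efficacy analyses to patients with all 6 infusions, and SAP 5.3.2 puts safety analyses on the Safety set. The six-infusion set for PHQ-9 is therefore an inference, but it is the only set the SAP offers for an efficacy endpoint.
4. A patient stopped for an adverse event before the sixth infusion gets no further dose and cannot enter that set. The same holds for a patient who stops early for any other reason.
5. If such a patient completes the Week 52 form, it is left out of the PHQ-9 analysis although the patient belongs to the Safety set.

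**What is displayed**

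- SAP 5.1.1 summarises continuous measurements by visit on observed data with minimum and maximum, and the results presentation in SAP 5.2.2 repeats this for secondary endpoints. A large worsening in total score can appear in the range. A change on one item cannot be identified there.
- SAP 5.3.2.2 ends the treatment-emergent period at the Week 42 visit or early withdrawal. Week 52 is the only post-baseline PHQ-9 visit. An event starting after Week 42 is not treatment-emergent, and the SAP sends such events to listings. A serious one might also reach the serious adverse event table, whose window is not stated.

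**Illustration of size**

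From the documents: 24 patients randomised 1:1, about 12 per arm. Assumed, not in the documents: a higher score is worse, the suicidal-thought item is scored 0 to 3, the SD of total-score change is 3 to 6, k of 12 patients in an arm stop early and have a Week 52 form, and they worsen by w points more than the others.

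*Analysis set.* If the six-infusion patients have mean change m, the all-treated mean is ((12 − k)m + k(m + w))/12 = m + kw/12. The gap is kw/12:

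| k | w = 3 | w = 5 | w = 9 |
|---|---|---|---|
| 1 | 0.25 | 0.42 | 0.75 |
| 2 | 0.50 | 0.83 | 1.50 |
| 3 | 0.75 | 1.25 | 2.25 |

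*Averaging.* One patient moving from 0 to 3 on one item, with nothing else changed, shifts the arm mean by 3/12 = 0.25 points. The standard error of the arm difference is SD × √(2/12), which is 1.22 at SD 3 and 2.45 at SD 6. The shift is 0.25/1.22 = 0.20 to 0.25/2.45 = 0.10 standard errors, too small to notice in a group result.

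*How often a stop for harm could occur.* With an assumed per-patient probability p, the chance of at least one among 24 is 1 − (1 − p)^24: 38% at p = 2%, 71% at 5%, 92% at 10%, 98% at 15%. This is the chance of a stopped patient, not of a lost form. A form is lost to the analysis only if that patient also completes Week 52.

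**The case against.** The strongest reply is that the patient at issue may have no Week 52 form. For participants who discontinue study treatment, the protocol describes safety follow-up by telephone or electronic contact. For those who do not complete the trial it describes an invitation to a visit about 30 days after the last treatment, with no PHQ-9 scheduled. The sentence about following all subjects to end of study stands in the paragraph on stopping or suspending the whole trial. Week 52 attendance after stopping infusions is therefore possible but not clearly assured. This stands: the loss is conditional on the form being completed, and the size is unknown.

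A reader might infer that a new suicidal thought would go unseen. The documents do not support that. The protocol places PHQ-9 within the investigator's examination at Week 0 and Week 52 and requires clinically significant findings to be recorded as adverse events. The SAP lists individual adverse events and bases safety analyses on the Safety set. What remains is narrower: no stated rule links a PHQ-9 answer to an adverse event, so this route depends on the investigator's judgement.

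A reader might also infer that the SAP expressly excludes early stoppers from PHQ-9, or analyses group means only. Section 5.3.1 names no set, and the observed-data summaries include the range. Nor would the plan report a misleading count of suicidal-thought cases, since it produces no such count.

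Neither document defines a suicidality endpoint or a worsening threshold, so an item-level display is a useful addition, not the repair of an error. The displays are detailed in a programming specification that is not among the documents. It might hold a PHQ-9 listing, but the choice of analysis set belongs in the SAP. Leaving out partly dosed patients is a general feature of the Efficacy set; it matters particularly here because PHQ-9 is assigned to safety.

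**Conclusion.** The concern holds as a mismatch between objective and analysis set. PHQ-9 is declared a safety measure and analysed under an efficacy heading, which by SAP section 4 implies six-infusion patients only. Early stoppers who complete Week 52 would be left out of a safety analysis, against the protocol's statement on treated subjects. Separately, no PHQ-9 analysis named in the SAP shows the suicidal-thought item.

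The gap of 0.25 to 2.25 points rests wholly on the assumed number of early stoppers with a form (1 to 3 of 12) and their extra worsening (3 to 9 points). With no such patient, the gap is zero. The primary efficacy result is unaffected. The change is worth making before unblinding because it is specific and cheap and stops tolerability from deciding who counts in a safety analysis.

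**What to change.** In SAP 5.3.2 or 5.3.3, state that PHQ-9 is summarised on the Safety analysis set (at least one dose, by treatment received), using all available post-baseline forms, with the number of patients without a Week 52 form shown by arm. Say explicitly how forms from unscheduled visits are used, because SAP 7.2.4 keeps these visits out of by-visit summaries.

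Add a patient listing of PHQ-9 total and suicidal-thought item at Week 0 and Week 52, with infusions received and any related adverse event. Keep the planned mean-change models as supplementary.

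The cost is SAP wording, one summary and one listing, with no new visits. Item responses may have to be taken from source forms, as the documents do not say whether they are in the database. Counts will be small and descriptive: the exact 95% interval for 1 of 12 is 0.2% to 38.5%, and for 0 of 12 it is 0% to 26.5%.

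Patients who leave before Week 52 are not recovered, because no PHQ-9 is scheduled at the roughly 30-day visit. They appear only in the count of missing forms. Adding PHQ-9 to that visit would need a protocol amendment and is a separate decision.
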